# 7. PLANNED ANALYSIS

The format of the listings and tables will follow the BI standards (6). The individual values of all patients will be listed. Listings will be sorted by treatment group, patient number and visit (if visit is applicable in the respective listing). The listings will be contained in Appendix 16.2 (SDL) of the CTR. If not stated otherwise, patients will be grouped by actual treatment received.

The following standard descriptive statistical parameters will be displayed in summary tables of continuous variables that are non-PK parameters:

N number non-missing observations

Mean arithmetic mean SD standard deviation

Min minimum Median median Max maximum

Tabulations of frequencies for categorical data will include all possible categories and will display the number of observations in a category, as well as the percentage (%) for each treatment group. Percentages will be rounded to one decimal place and will be based on all patients in the respective subject set whether they have non-missing values or not. The category 'missing' will be displayed only if there are actually missing values.

# 7.1 DEMOGRAPHIC AND OTHER BASELINE CHARACTERISTICS

Only descriptive statistics are planned for this section of the CTR, based on the TS.

The data will be summarized by treatment group and in total.

# Demographics:

Sex, ethnicity, race, age [years], age (categories), height [cm], weight [kg] and BMI [kg/m²], history of substance use (tobacco, nicotine, vaping products, alcohol, cannabis), UGT2B17 genotype.

BMI will be calculated as weight  $[kg]/(0.01 * height [cm])^2$ .

# Baseline characteristics:

Pharmacogenetic results of UGT2B17 genotype will be reported as: \*1/\*1 or \*1/\*2.

# 7.2 CONCOMITANT DISEASES AND MEDICATION

Only descriptive analysis by treatment group is planned for this section of the CTR.

Baseline conditions / concomitant diagnoses will be summarized by Medical Dictionary for Regulatory Activities (MedDRA) system organ class (SOC) and preferred term (PT).

Concomitant medication taken at baseline or during the treatment period will be summarized by World Health Organization-Drug Dictionary (WHO-DD) ATC3 class and PT. Previous concomitant medication, i.e. those taken and stopped prior to entering the treatment period, will be listed only.

All data will be coded using the most recent versions of WHO-DD and MedDRA dictionaries.

The relevance of the concomitant therapies to the evaluation of PD and PK will be decided no later than at the RPM.

#### 7.3 TREATMENT COMPLIANCE

Treatment compliance will be listed and descriptive statistics for each assessment day will be displayed by treatment group. Deviations from planned intake will be addressed in the RPM (refer to Section 6.2) and relevant deviations will be described in the CTR.

Treatment compliance (yes/no) will be based on the adherence to the expected range of 80-120% for number of tablets actually taken vs. number of tablets which should have been taken as directed by the investigator, see CTP Section 4.3.

# 7.4 PRIMARY ENDPOINT

# 7.4.1 Primary analysis of the primary endpoint

The primary endpoint (cf. Section 5.1) will be derived according to BI standards (7) and (8). The proportion of patients with at least one treatment emergent drug-related AE per treatment group will be calculated. The analysis will be based on the TS and will be descriptive in nature.

#### 7.5 SECONDARY ENDPOINTS

# 7.5.1 Secondary endpoints

The primary analysis of the secondary endpoints listed in Section 5.2.2. will be descriptive in nature and will be based on the TS.

For biomarkers determined on sputum the mean of all available valid samples which are within the analysis time window, will be used as Week 12/EoT value in the analyses. Actual observed values at these visits will only be listed.

Descriptive statistics of absolute values as well as changes from baseline (refer to Section 6.7) and percent changes from baseline (if applicable) will be presented by planned time point for the secondary endpoints.

For NE activity in zymosan stimulated blood, neutrophil counts measured from safety lab will be used for normalisation of NE activity when collection time points match. Otherwise, the

TSAP for BI Trial No: 1405-0008 Page 19 of 25
Proprietary confidential information © 2022 Boehringer Ingelheim International GmbH or one or more of its affiliated companies

neutrophil count from the time point closest to sampling for NE activity assessment will be used for normalisation. The derivation detail of NE activity in whole blood is in Section 9.1

The assessment of NE activity in sputum and blood will further comprise the analysis of the % inhibition of NE activity. For each time point including baseline, % inhibition will be calculated as:

$$NE \% inhibition_t = \frac{NE \ activity_{baseline} - NE \ activity_t}{NE \ activity_{baseline}} \times 100$$

Descriptive statistics of maximum NE % inhibition (on patient level) will be presented by dose group. Individual line plots over time by dose group will be presented.

Individual NE activity data will be listed including % inhibition in sputum, % inhibition in blood, neutrophil count normalised and UGT2B17 genotype.

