Duration of treatment	84 days: In Part A, 83 days twice daily (bid) and single dose on day
	84; in Part B, 84 days once daily (qd)
Statistical methods	The primary and secondary endpoints will be evaluated using
	descriptive statistics.

Page 5 of 111

Proprietary confidential information © 2021 Boehringer Ingelheim International GmbH or one or more of its affiliated companies

MAIN FLOW CHART

Trial Periods	Screening ¹	Ru (Bas B	n-in eline - SL)	Randomised Treatment Period							Follow- up (FUP)		
Visit ²	1	2a BSL	2b BSL	3 ³	4 ¹⁵	5	6 PK Day	7 ¹⁶	8	9a	9b	10 EoT / early EoT ⁴	11 FUP / EoS
Week	-4	-1		0	1	2	4	6	8	11		12	14
Day	-27	-6	-2	1	8	15	29	43	57	78	82	84	98
Time window for visits (days)	+14	+2	+1	±0	±3	±3	±3	±3	±3	+3	+1	+3	±4
Informed consent	X												
Demographics	Х												
Medical history including Smoking status and alcohol history	x												
Testing for UGT2B17 genotype	X												
Physical examination	Х			Х			Х					Х	X
Height (only at V1)/ body weight	X			X			X					X	X
Vital signs: pulse rate (PR), blood pressure (BP), aural body temperature	X			X		X	X		X			X	x
Laboratory tests (blood/urine)	X ¹³			X		X	X	X	X			X	X
12-Lead Electrocardiogram (ECG) (single ECG, may be repeated by investigator judgement)	Х			X		x	X		x			X	
Pregnancy test in women (serum S / urine U)	X (S)			X (U) ⁵					X (U) ⁵			X (U) ⁵	
Concomitant therapy	X	X	X	X	X	X	X	X	X	X	X	X	X
Review of in-/exclusion criteria	X	X	X	X									
Randomisation				Х									

Boehringer Ingelheim BI Trial No.: 1405-0008 c31693972-02

Clinical Trial Protocol

Page 6 of 111

Proprietary confidential information © 2021 Boehringer Ingelheim International GmbH or one or more of its affiliated companies

Trial Periods	Screening ¹	Ru (Bas B	in-in eline - SL)				Randomis	ed Treat	ment Peri	iod			Follow- up (FUP)
Visit ²	1	2a BSL	2b BSL	3 ³	4 ¹⁵	5	6 PK Day	7 ¹⁶	8	9a	9b	10 EoT / early EoT ⁴	11 FUP / EoS
IRT call/notification ¹²	X			X		X	X		X			X	
Administer trial drugs at site ⁶				Х			X						
Dispense trial drugs for home ⁶				Х		X	Х		Х				
PK blood sampling (see Sample and Assessment Flow Chart)				X		X	X					X	
Lung questionnaires (QoL-B; SGRQ; CASA-Q)			X						X			X	
Sputum (collected at site) ^{7, 14}	X ¹⁷	Χ	Χ	Χ		X	X		X	X	X	X	X
24h Sputum (collected at home) ⁸				X			X					X	
Murray sputum colour chart			Χ	X								Х	
NEATstik [®] (NE determination)		Χ	Χ									X	
Blood sample for biomarkers, pharmacodynamic (PD)			X	Х		X	X		X			X	X

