6. INVESTIGATIONAL PLAN

6.1 **VISIT SCHEDULE**

The study scheme, including all visits, is shown in Section 3.1, Figure 3.1: 1.

Screening Visit 1 will be done at least 7 days prior to Baseline (BSL) Visit 2a. During BSL (V2a, V2b, V3), there will be a minimum of two and up to three valid sputum samples within indicated timeframes. The End of Treatment (EoT) Visit 10 will be done 12 weeks after randomisation. Prior to EoT, during V9 and V10, i.e. Day 78-82 and EoT, two to three valid sputum samples will be obtained within seven days.

The acceptable time windows for screening, for measurements and assessments are provided in the main Flow Chart and are also described in the Section 6.2 below.

The Sample and Assessment Flow Chart provides sputum, PK and PD details for timing of sampling as well as conduct of lung function meassurements and questionnaires. Planned blood sampling times should be adhered to as closely as possible.

The acceptable deviation from the scheduled time for vital signs, ECG, PK and laboratory tests will be \pm 15 min. The exact times of trial visit assessments and measurements outside the permitted time windows will be documented in the eCRF.

If a patient misses an appointment, it will be rescheduled if possible. The relevance of measurements outside the permitted time windows will be assessed no later than at the Report Planning Meeting.

In exceptional circumstances during COVID-19 pandemic, when it is impossible to conduct study visits at the study site, study visits may be performed at patient's home or remotely (via telephone and/or internet based means of communication). Visits may also be performed as a hybrid of home and remote visit. All home/remote visits need to be discussed with and authorised by the sponsor's trial team. The trial team's decision will be based on a thorough benefit-risk evaluation.

The procedures performed during a home/remote visit may be adjusted as compared to a regular visit, as detailed in Appendix 10.4

All COVID-19 related deviations from the original schedule of visits and procedures will be documented and the implications considered for the analysis of the trial data.

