adequate sputum sample is produced spontaneously, induction of sputum with isotonic, or subsequently hypertonic saline is mandatory. If sputum samples do not meet the quality criteria as directly assessed at the site, re-sampling at the next day is generally possible. An instruction on sputum handling will be provided to the site in the ISF.

If treated with bronchodilators, wash-out of 24 hours for qd long acting, 12 hours for bid long acting, and 8 hours for short acting bronchodilators should be observed before pulmonary function tests.

The safety measurements performed during the treatment period are specified in Section 5.2 of this protocol and in the Flow Chart. For details on times of all other trial procedures, refer to the Flow Chart.

AEs and concomitant therapy will be assessed continuously from screening until the end ofstudy.

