7.2.3 Secondary endpoint analyses

The analysis of the secondary endpoints, see Section 2.1.3, will be based on the TS. Data from of all timepoints except those that were sampled within 15 days after the end of an exacerbation will be included in the analysis.

The 'baseline' and 'after 12 weeks' value of parameters that are measured more than once for these time points, see Sample and Assessment Flow Chart, will be derived as the mean of the available valid samples at each of these time points.

The change from baseline of NE activity in sputum at the different visits (X) is calculated as: cfb in NE activity at Visit X = NE activity at Visit X - NE activity at baseline.

For the derivation of the change from baseline of NE activity in blood, the NE activity in blood at each visit will first be normalized to neutrophil counts and then the change from baseline is determined analog to the NE activity in sputum above.

The secondary endpoints will be primarily analysed by descriptive statistics and graphical representations across all visits.

Page 81 of 111

Proprietary confidential information © 2021 Boehringer Ingelheim International GmbH or one or more of its affiliated companies

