# 6.7 BASELINE, TIME WINDOWS AND CALCULATED VISITS

For all parameters, except for biomarkers, baseline is defined as the last non-missing value prior to first administration of the trial treatment. In case of planned multiple measurements of biomarkers within the run-in period prior to first drug administration (e.g. at Visit 2a, 2b or 3), the following will apply:

Measurements taken after first administration of trial treatment will be considered either onor off-treatment values based on the definition in Table 6.1: 1, and will be assigned to visits for statistical analysis, if applicable, as defined below.

Analysis of AE data (including findings in 12-lead ECG assessments or physical examinations), potentially clinically significant abnormal laboratory values, concomitant medication or non-drug therapies will not be based on visits. Frequency tables for AE data will be using on-treatment data and categorized based on their occurring/starting dates. Therefore, no assignment to time windows will be necessary for such data.

Analysis day is calculated as follows:

If assessment date and time is prior to the date and time of first study drug intake: Date of assessment – date of first study drug intake

If assessment date and time is greater or equal to the date and time of first study drug intake: Date of assessment – date of first study drug intake +1 day

Analysis visit windows for other assessments during the study are given in the following tables. The date of the first drug intake will be used as study day 1 for the time windowing (including planned first drug administration visit V3 and repeated V3). If more than one value is available within one time window the one which is closest to the planned time/day is used for analysis. In case two values are equidistant from the planned time/day, then the last one will be picked.

TSAP for BI Trial No: 1405-0008 Page 16 of 25

Proprietary confidential information © 2022 Boehringer Ingelheim International GmbH or one or more of its affiliated companies

Time windows for assignment of safety assessment – laboratory Table 6.7: 2

			Time window [days]		
Visit			Window	Start	End
number	Visit label	Planned	per CTP	(analysis)	(analysis)
(CTP)	(analysis)	Day			
V1	Screening	-27	± 14	All pre-baselin	e measurements
V3	Baseline	1	$\pm 0$	NA	Date/time of first
					administration of
					study drug
V5	Week 2	15	$\pm 3$	Start of on-	22
				treatment phase	
				as defined in	
				table 6.1.1	

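### By-visit sputum summaries set a Week 12 mean of two to three samples beside single samples at Weeks 2, 4, 8 and follow-up; with right-skewed data the medians and spread are not comparable across visits

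*SAP*

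**What the plan says.** **Derivation.** For biomarkers measured in sputum, SAP 7.5.1 states that "the mean of all available valid samples which are within the analysis time window, will be used as Week 12/EoT value". Protocol 7.2.3 applies the rule to both ends of the comparison: baseline and Week 12 values "will be derived as the mean of the available valid samples at each of these time points".

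**Number of samples.** For baseline (V2a, V2b, V3), Protocol 6.1 says that "there will be a minimum of two and up to three valid sputum samples within indicated timeframes". For the end of treatment (V9a, V9b, V10), "two to three valid sputum samples will be obtained within seven days". The flow charts schedule one site sputum collection at each of V5 (Week 2), V6 (Week 4), V8 (Week 8) and V11 (follow-up). A repeat collection replaces a failed sample and is not a planned replicate: "If sputum samples do not meet the quality criteria as directly assessed at the site, re-sampling at the next day is generally possible" (Protocol 6.2.2). The general rule in SAP 6.7 also selects one value and does not average: "If more than one value is available within one time window the one which is closest to the planned time/day is used for analysis".

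**Display.** Protocol 7.2.3 says: "The secondary endpoints will be primarily analysed by descriptive statistics and graphical representations across all visits". SAP 7.5.1 summarises absolute values, changes and percent changes at each planned time point. It adds % inhibition against baseline, each patient's maximum % inhibition, and individual line plots. SAP 7 names mean, SD, minimum, median and maximum as the summary statistics. At the averaged visits, the single observed values go to listings only.

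**What cannot be read.** The body of SAP Table 6.7: 1 (biomarker baseline), Section 5.3.2 and Section 9 are absent from the public text. The baseline rule used here is therefore the protocol's. Both documents say only mean for the per-patient average. Arithmetic is the natural reading, but it is not written out.

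**The concern.** Sampling intensity changes with time on drug. A Week 12 value pools up to three collections, and a Week 2, 4 or 8 value is one collection. Both are compared with the same averaged baseline and appear next to each other in the same tables and plots.

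For a right-skewed measurement, the median of one sample lies below the median of an arithmetic mean of several. A patient whose true level never changes then tends to look a little inhibited at the single-sample visits and not at Week 12. An arm with constant inhibition can look as if its effect weakens at the visit that matters most.

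The secondary objective centres on sputum NE activity (Protocol 2.1.1), and Protocol 1.3 intends the results to inform the choice of dosing regimen. The shape over time will be read. No planned summary lets the reader compare Week 12 with Weeks 2 to 8 on equal terms.

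**Working it through.** The plan states no figure on this point, and Protocol 7.5 bases the sample size on no power calculation, so there is nothing to reproduce.

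**Inputs from the documents.** Two to three samples at baseline and Week 12, one at V5, V6, V8 and V11. Groups of 9 (placebo), 9 (30 mg bid) and 18 (150 mg qd).

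**Assumptions.** The documents give no within-patient distribution or SD for sputum NE; Protocol 3.3.1 mentions only potentially high variability. I take multiplicative log-normal sample noise with ln-SD 0.3, 0.5, 0.8 or 1.2, independent between samples, and a constant true inhibition t.

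**Median % inhibition.** With three samples B at baseline:

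- single-sample visit: R = X / mean(B1, B2, B3)
- Week 12: R = mean(W1, W2, W3) / mean(B1, B2, B3)
- median inhibition = 100 × [1 − (1 − t) × median(R)]

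At Week 12, numerator and denominator have the same distribution, so median(R) = 1 and the displayed median equals the truth. At a single-sample visit, simulation (400,000 patients per setting) gives median(R) of about 0.972, 0.925, 0.824 and 0.671. For example, at t = 50% and ln-SD 0.5: 100 × (1 − 0.5 × 0.925) = 53.8%.

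| True inhibition | Single-sample visit, ln-SD 0.3 / 0.5 / 0.8 / 1.2 | Week 12 |
|---|---|---|
| 0% | 2.8 / 7.5 / 17.6 / 32.9% | about 0% |
| 50% | 51.4 / 53.8 / 58.7 / 66.3% | 50% |
| 90% | 90.3 / 90.8 / 91.8 / 93.3% | 90% |

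With two replicates at each end, the 50% row becomes 51.0 / 52.8 / 56.7 / 62.4% against 50%. With three baseline samples but only two at Week 12, Week 12 itself shows about 2 / 5 / 11% at no effect for ln-SD 0.5 / 0.8 / 1.2.

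**Sensitivity.**

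- If half of the log variance is shared by samples from the same week, the no-effect shift roughly halves, to about 1.6 / 3.8 / 9.5 / 19.5%.
- With symmetric noise, the median does not move (49.97% against 50.0% at t = 50%).
- Group arithmetic means do not move in any setting.

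**Spread.** The sampling-noise variance of absolute change is proportional to (1 − t)²/m + 1/3, where m is the number of samples at the visit. The SD ratio of a single-sample visit to Week 12 is therefore √{[(1 − t)² + 1/3] / [(1 − t)²/3 + 1/3]}:

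- t = 0: √(1.333/0.667) = 1.41
- t = 50%: √(0.583/0.417) = 1.18
- t = 90%: √(0.343/0.337) = 1.01

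These ratios describe sampling noise. Once between-patient variation is included (assumed ln-SD 1.0), the ratio at t = 50% and ln-SD 0.8 is 3.085/2.745 = 1.12. The interquartile range of % inhibition at no effect is wider at single-sample visits for ln-SD 0.3 and 0.8 (46 against 34, 111 against 98) but reverses at 1.2 (150 against 161).

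**At the trial's group sizes.** With constant 50% inhibition, Week 12 shows the lowest median of the four on-treatment visits in 27 / 32 / 40 / 47% of trials at n = 9 and 30 / 38 / 48 / 60% at n = 18. Like-for-like visits would give 25%.

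**Maximum % inhibition.** Under a constant effect, a patient's maximum falls at the averaged Week 12 visit in about 11 to 16% of patients, against 25% if all four visits were alike.

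**The case against.** The strongest reply is that the secondary endpoint is untouched. It compares a mean of two to three samples with another such mean, and extra sampling at those two times is a deliberate and sensible choice. That stands. A reader might infer that the Week 12 result is biased, but the documents do not support this when sample counts match.

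A reader might also infer that the medians must move because the sample counts differ. They need not: the shift requires right-skewed variation within patients. Skew is plausible for activity and count data bounded at zero, but the documents neither state nor quantify it. Only unequal averaging follows from the schedule alone, and its effect on spread depends on scale and effect size.

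Nor do the documents support a prediction that an active arm will appear to lose its effect. At 90% inhibition the shift is 0.3 to 3.3 points, and replicates taken within about a week probably share some variation, which reduces it. Protocol 4.1.2 treats trough inhibition above 90% in blood as the potentially useful level. Sputum inhibition is unknown, however, and Protocol 3.2 notes that earlier inhibitors did not reach high suppression in the airways, so modest inhibition is a realistic case.

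Placebo carries the same proportional shift, so a same-visit comparison would expose it. This holds in principle, but SAP 6.1 analyses placebo by part (12 × 1/4 = 3 and 24 × 1/4 = 6 patients) and pools only if that is judged appropriate. Finally, the replicates are listed and the trial is exploratory. That limits the consequence, though a listing does not replace a comparable summary.

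**Conclusion.** The point holds as one about comparability across visits. The documents establish the unequal number of samples, the side-by-side display and the absence of a like-for-like summary. The median shift rests on right-skewed within-patient variation. Under the independent log-normal assumption with three replicates, the gap between single-sample visits and Week 12 is about 3 to 33 points with no effect, 1 to 16 points at 50% inhibition, and 0.3 to 3.3 points at 90%. It is smaller with two replicates or with variation shared within a week.

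The problem is confined to by-visit medians, spread, plots and the patient-level maximum % inhibition. The baseline-to-Week-12 endpoint remains like for like when sample counts match. This is a cheap improvement to the display and does not call for a new main derivation.

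**What to change.** Keep the averaged baseline and Week 12 values for the secondary endpoint. In SAP 7.5.1, add:

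1. To the by-visit tables and plots, a series with one sample per visit: V3 pre-dose as baseline, then V5, V6, V8, V10 and V11. With one sample on each side, X/B has median 1 under no change whether or not the noise is skewed, so the artefact disappears. State which sample stands in when V3 or V10 is invalid, because the protocol requires only two valid samples at each end.
2. The maximum % inhibition computed from that same series.
3. The number of samples behind each displayed value, and the scale on which replicates are averaged.

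A geometric mean of the replicates could be shown as an optional sensitivity display. It aligns the medians under log-normal noise, but it needs a rule for zero or unquantifiable values. It also leaves spread unequal: the SD of log change stays √[(1 + 1/3)/(2/3)] = 1.41 times larger at single-sample visits. For these reasons it should not replace the main derivation.

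The cost is one extra summary and plot from data already collected. The added series is noisier: its log-change SD is √2 = 1.41 times the sample ln-SD, against √(2/3) = 0.82 for the averaged Week 12 change. It should support the endpoint analysis and not displace it.

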3.2 DISCUSSION OF TRIAL DESIGN, INCLUDING THE CHOICE OF CONTROL GROUP(S)

Since this trial evaluates BI 1323495 for 12 weeks (compared to 10.5 days – for bid dose groups, or 11 days – for the qd dose group in the healthy volunteer MRD trial) and for the first time in a patient population up to a higher age, safety and tolerability is the recommended primary objective for assessing a new drug in patients with nCFB. Due to its mechanism of action, a 12-week treatment period is considered sufficient to evaluate the PK and PD, and to potentially obtain an early sign of clinical efficacy of BI 1323495. A 2-week follow-up period without treatment is considered to be sufficient, as this covers twice the residual effect period during which BI 1323495 exposures are expected to return to not quantifiable levels and pharmacodynamic effects (inhibition of NE) are expected to have fully reversed.

Each trial part has a parallel-group, randomised, double-blind and placebo-controlled design as this is considered the most appropriate design to assess safety and efficacy of different doses of BI 1323495. In this trial, a double-blind (patient and investigator blinded, sponsor unblinded - for details refer to Section 4.1.5) concept was chosen to reduce the bias with regard to treatment-dependent effects as much as possible. Due to a close safety monitoring, this approach is considered acceptable for patients. A placebo group is included in order to control for safety, tolerability, and pharmacodynamic effects of the trial medication.

Only UGT2B17 extensive metabolizers will be included in this study to reduce PK variability. A dose of 30 mg bid BI 1323495 has been shown to be safely tolerated and was associated with a median level of >90% inhibition of NE at trough in blood of a healthy volunteer population of UGT2B17 EMs. Of note, in addition, according to preliminary pharmacometric simulations, a dose of 30 mg bid is predicted to remain within the exposure boundaries defined based on the results of the non-clinical toxicity studies even in UGT2B17 PMs who are expected to have BI 1323495 exposures exceeding those in EMs. Therefore, this dose level might be compatible later in clinical development with a mixed population of both PMs and EMs (beyond the scope of this trial). As such, this dose could be a therapeutic dose for EMs and PMs alike.

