Total daily doses exceeding the dose of 150 mg qd to be investigated in Part B were confirmed to be safe and tolerated in the MRD trial in healthy volunteers, and at 150 mg qd it is not expected that exposures in individual patients may exceed exposure boundaries that were predefined based on the NOAEL in animal toxicity studies. This dose is expected to achieve the maximal pharmacodynamic effect. A dose associated with a pharmacodynamic effect approaching complete suppression of NE activity in blood is considered important as previous trials with other NE inhibitors have failed to achieve a high level of NE suppression in the airways despite adequate suppression in blood.

Based on information collected during the conduct of Parts A and B of this trial, it may be decided by the sponsor that important additional insights could be obtained from an additional part to introduce a third (intermediate or lower) dose level. This may be addressed in a subsequent substantial amendment.

Boehringer Ingelheim		22 Apr 2021
BI Trial No.: 1405-0008		
c31693972-02	Clinical Trial Protocol	Page 47 of 111

The start of each trial part is chosen to efficiently evaluate the overall trial objectives given the staggered availability of data from the MRD trial 1405-0002 and represents a careful and safety conscious approach to the treatment of nCFB patients with BI 1323495. Periodic analyses of trial data (for details see Section 7.2.7) will provide valuable results based on the actual study population.

A total sample size of up to 36 patients, with N=12 in Part A and N=24 in Part B, is considered sufficient to assess the main objectives of this exploratory trial.

The final analysis of this trial will be based on data from all trial parts, resulting in a sample size of possibly 9 - 18 patients per treatment group. Data from patients treated with placebo from both trial parts will be pooled for the purpose of comparison with the two active treatment groups. The potential risk for bias due to combined analysis is thereby seen as low, as the unblinded periodic analysis results will not be shared with the staff at trial sites. Also, the time lag between the investigations of a specific treatment group from one trial part to the other is not expected to introduce bias in the data.

The overall feasibility of the trial is considered given, as experienced investigators will be selected that have both, access to nCFB patients as well as sputum handling proficiency.

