4.1.2 Selection of doses in the trial and dose modifications

The 30 mg bid dose of BI 1323495 is a confirmed safe and tolerated dose after multiple dosing in healthy volunteers and could potentially be a therapeutic dose that is applicable for both, EMs and PMs, and will thus be tested in Part A. In the MRD trial 1405-0002, with 30 mg bid in EMs, median trough NE inhibition at steady state exceeded 90% which is considered a PD effect size potentially associated with a clinical benefit if maintained long term (Table 1.2.3.2: 1). The 150 mg qd dose of BI 1323495 selected for Part B was based on safety/tolerability data from higher dose groups of the healthy volunteer MRD study and is anticipated to reach the maximal safely achievable PD effect. This dose was selected to ensure that exposures will not exceed a gMean value that was observed and safely tolerated in the MRD trial 1405-0002, and to not exceed exposure boundaries that were predefined based on animal toxicity studies (see Section 1.2.2.4). Doses will be administered with food containing a fat component.

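### The patient-level maximum of NE % inhibition (SAP 7.5.1) is biased upward, most on placebo, with no visible on-treatment limit; placebo pooling, stated in protocol 3.2, is only optional in SAP 6.1

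*SAP*

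**What the plan says.** SAP 7.5.1 makes the descriptive analysis of the secondary endpoints the main one. It then adds: "The assessment of NE activity in sputum and blood will further comprise the analysis of the % inhibition of NE activity". The derivation is introduced with "For each time point including baseline, % inhibition will be calculated as", and the by-group summary under that name is "Descriptive statistics of maximum NE % inhibition (on patient level) will be presented by dose group". Individual line plots and listings accompany it.

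The same section also plans absolute values, changes and "percent changes from baseline (if applicable) will be presented by planned time point for the secondary endpoints". The Week 12 sputum value is the mean of the valid samples in its window.

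The protocol supports 30 mg bid with a trough figure. Section 3.2 says the dose was "associated with a median level of >90% inhibition of NE at trough in blood", and section 4.1.2 says "median trough NE inhibition at steady state exceeded 90% which is considered a PD effect size potentially associated with a clinical benefit". For 150 mg qd, section 3.2 says "This dose is expected to achieve the maximal pharmacodynamic effect".

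On placebo, protocol 3.2 states: "Data from patients treated with placebo from both trial parts will be pooled for the purpose of comparison with the two active treatment groups". SAP 6.1 instead analyses placebo patients by trial part and adds a pooled group only at discretion.

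**The concern.** A maximum over several noisy measurements tends to pick the luckiest one. It exceeds the patient's true level on average, and more so with more values. The number of values will differ between patients: SAP 6.6.2 drops late-processed sputum and data after restricted medication, and protocol 7.2.3 drops samples taken within 15 days after the end of an exacerbation.

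Three things could mislead a reader of this table.

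- Placebo would show apparent inhibition where there is none, which shrinks the visible contrast with active drug.
- An active group's maximum could be set against the 90% mark, which is a trough figure. In blood, the maximum will tend to come from samples taken after dosing.
- The visible text does not say which time points count. The formula is applied at baseline, and the Sample and Assessment Flow Chart schedules blood PD and sputum at V11, about two weeks after the last dose. SAP Table 6.1: 1 defines an on-treatment phase that covers biomarkers, but the maximum is not tied to it.

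The optional pooling matters for the same displays, because it decides whether the reference group has 9 patients or is split into 3 and 6.

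**Working it through.** **The plan's own figure.** Protocol Table 1.2.3.2: 1 gives 30 mg bid a median trough inhibition of 91.8% (n = 8, range 80.4 to 93.4), which is above 90% as claimed. After dosing the median is 95.1%, so the gap is 95.1 − 91.8 = 3.3 points. For 120 mg qd it is 98.0 − 93.1 = 4.9 points.

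**Identity.** With B the baseline and A the later activity, % inhibition = 100 × (B − A)/B and percent change = 100 × (A − B)/B. One is the other with the sign reversed.

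**Blood noise.** The multiple-dose trial's placebo trough range is −41.3 to 36.6 (n = 16). The expected range of 16 normal values is 3.53 SD, so the SD is about 77.9/3.53 = 22 points. If the baseline is a mean of two values, the log-SD is about 0.22/√1.5 = 0.18. If it is a single value, it is about 0.22/√2 = 0.16. I used 0.15 and 0.18, with 0.23 as a high case.

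**Simulation.** 400,000 patients per case, with independent lognormal noise within patients.

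*Blood:* baseline mean of 2 (V2b, V3); maximum over V5, V6 pre-dose, V6 at 6 h, V8 and V10. Median maximum (%):

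| True inhibition | log-SD 0.15 | 0.18 | 0.23 |
|---|---|---|---|
| 0 | 16.3 | 19.3 | 24.2 |
| 88 | 89.9 | 90.3 | 90.9 |
| 90 | 91.6 | 91.9 | 92.4 |
| 98 | 98.3 | 98.4 | 98.5 |

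The contrast at a true 90% against placebo should be 90 points. On the maximum it is 91.6 − 16.3 = 75.3, 91.9 − 19.3 = 72.6 and 92.4 − 24.2 = 68.2.

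With the 30 mg bid levels from the protocol table (91.8 at trough, 95.1 after dosing), V6 pre-dose has a median of 91.8 to 91.9%. The median maximum is about 95.1 to 96.2%, depending on the log-SD and on whether V5, V8 and V10 sit near trough or near the post-dose level. The maximum therefore describes the post-dose level.

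*Sputum:* baseline mean of 3; values are the Week 12 mean of 3 plus one, two or three single visits. The documents give no sputum variability, so the log-SDs are assumptions. Median maximum (%):

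| True inhibition | Values | log-SD 0.3 | 0.5 | 0.7 |
|---|---|---|---|---|
| 0 | 2 | 13 | 23 | 32 |
| 0 | 3 | 21 | 34 | 46 |
| 0 | 4 | 26 | 41 | 53 |
| 0 | 4, plus baseline and V11 | 29 | 45 | 58 |
| 50 | 2 | 57 | 61 | 66 |
| 50 | 4 | 63 | 70 | 77 |
| 80 | 2 | 83 | 85 | 86 |
| 80 | 4 | 85 | 88 | 91 |

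The Week 12 mean alone has a median of 0, 50 and 80% in these cases. At log-SD 0.5 with 4 values, the contrast with placebo is 70 − 41 = 29 points instead of 50, and 88 − 41 = 47 instead of 80.

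**Placebo groups.** 12 × 1/4 = 3 in Part A and 24 × 1/4 = 6 in Part B, 9 in all. With no effect and log-SD 0.5, the 95% sampling range of the group median Week 12 sputum % inhibition is about −74 to 43% with 3 patients, −47 to 31% with 6 and −40 to 29% with 9.

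**The case against.** Much of this is already handled. Because percent change is % inhibition with the sign reversed, the by-time-point table carries the same information, including V6 pre-dose blood and the Week 12 sputum mean. That stands. What remains open is only that percent change is conditional on being applicable and that V6 pre-dose is not labelled as trough.

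The maximum has a legitimate use. It was reported in the multiple-dose trial (protocol 1.2.3.2) and fits the Part B rationale of maximal effect. Trough inhibition is not an endpoint here. This also stands, so the maximum should be kept and labelled, not dropped.

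SAP sections 5.3.2, 7.6 and 9.1 and the body of Table 6.7: 1 are not visible and may name the time points. SAP 6.7 does classify post-dose measurements as on- or off-treatment. So it cannot be asserted that the plan leaves the time points undefined or that V11 will be counted, only that the visible text sets no limit. Counting baseline and V11 adds 3 to 5 points in the no-effect sputum case. It would hardly matter in a strongly inhibited group, whose maximum comes from an on-treatment sample anyway.

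The noise model assumes independent errors and treats all the placebo spread as within-patient. Positive correlation between visits, or some between-patient spread, would make the bias smaller.

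**Conclusion.** The point holds at the lowest severity. The maximum overstates inhibition within every group. In blood the bias is about 2 points at a true 90% and under 1 point at 98%, but about 16 to 24 points with no effect. In sputum it is about 26 to 53 points with no effect and four values, if the assumed log-SDs of 0.3 to 0.7 are realistic. A constant true blood inhibition of 88% gives a median maximum of about 90 to 91%, so this statistic cannot show whether the 90% trough benchmark is met.

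A reader might infer more than the documents support:

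- **That the bias flatters the drug.** Against placebo it does the reverse, because placebo is inflated most.
- **That trough or Week 12 inhibition will go unreported.** The by-time-point summaries already cover both.
- **That a trial conclusion is at risk.** No test or decision rule uses the maximum, and the week 12 endpoint does not involve it.
- **That a maximum always separates regimens less well than trough.** In the multiple-dose trial, 30 mg bid and 120 mg qd differ by 98.0 − 95.1 = 2.9 points after dosing and 93.1 − 91.8 = 1.3 at trough.

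The placebo difference is separate and does not depend on the simulation of the maximum: the protocol commits to pooling and the SAP makes it optional.

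**What to change.** In the SAP:

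1. Make the pooled placebo group (9 patients) a required display beside the by-part display of section 6.1, as protocol 3.2 states.
2. In section 7.5.1, restrict the maximum to the on-treatment phase of Table 6.1: 1, without baseline and V11. List the time points, label the result supportive, and give the number of values per patient.
3. Confirm that the by-time-point percent-change table, or equivalently % inhibition, will be produced for NE activity. Label blood at V6 pre-dose as trough and show sputum at the Week 12 mean.

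This changes SAP text and programming only, with no new data and no change to an endpoint. The cost is one or two extra tables. The trough summary would rest on one scheduled sample per patient, because V6 is the only on-treatment visit with blood PD explicitly scheduled before dosing.
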